# **RESEARCH PLAN**

### A. Specific Aims

**Hypothesis:** We hypothesize that two sessions of 10 days of RT-CGM in the setting of nutrition and physical activity counseling coupled with education on how exercise and nutrition affect blood sugar levels will promote weight loss in participants with prediabetes and diabetes and reduce glycemic variability.

**Aim 1**: Examine the effect of two 10-day sessions of RT-CGM over 6 weeks on weight loss, change in body composition, activity level and nutritional changes in subjects with diabetes and prediabetes 12 weeks later.

Aim 2: Evaluate participants' perception of RT-CGM as a weight loss tool.

**Aim 3**: Evaluate the effect of RT-CGM on glycemic variability in subjects with prediabetes and diabetes.

### **B. Background and Significance**

In the United States, more than 29 million people have diabetes and 86 million adults have prediabetes (1). Annual medical costs for persons with diagnosed diabetes average \$13,000, with approximately \$7,900 being directly attributable to the disease (2). Many comprehensive lifestyle intervention programs such as the Diabetes Prevention Program (DPP) (3) and behavior change strategies (alone or in combination) have been used to promote weight loss in obese, high-risk individuals with variable effects. These include motivational interviewing, accountability/self-monitoring programs, food journals (4-6), pedometers (7, 8) and mobile phone apps (9) for weight loss.

There is widespread acknowledgment that lifestyle behavior change is critical for weight and glucose regulation. The National Institute of Diabetes and Digestive and Kidney Diseases' DPP trial (3) demonstrated that lifestyle changes (diet and physical activity aimed at weight loss) were more effective than metformin in preventing diabetes among those with prediabetes (6); however, the DPP lifestyle intervention involved frequent visits and coaching over several years, which is costly and labor intensive. More scalable adaptations for community translation, such as a 12-session group-based program called Group Lifestyle Balance™ (GLB) have been shown to be effective in community settings. A recent meta-analysis conducted in 2012 reviewing 28 DPP translational interventions had an average weight loss of 4%. However, the attrition rate or drop-out rate was as high as 50% in some programs and weight loss was highly dependent on number of core sessions attended (10). In a pilot project that we just completed in conjunction with the George Washington Milken Instituteof Public Health with younger African-American women, the drop-out rate was 35% and participation mean was 5.5 (range 2-11) for the 12 core sessions and the need to evaluate alternative, self-directed behavior change

methods to promote weight loss. Thus, we propose to evaluate the utility of RT-CGM, an emerging technology that holds promise as a behavior modification tool to promote weight loss and lifestyle changes in those with obesity, prediabetes or diabetes.

Several studies have demonstrated that encouraging patient engagement enhances self-care behaviors such as healthy eating (12-15). Patients are more likely to engage in healthy behaviors when they are given appropriate tools and are supported by their clinicians. For example, structured self-monitoring of blood glucose (SMBG) by 7-8 fingersticks a day has been shown to improve glycemic control in patients with diabetes by helping them understand glycemic response to food and activity (16). However, this is nearly impossible to reproduce in a real-world setting because of the inconvenience of performing SMBG and the discomfort associated with multiple fingersticks. The technology of CGM uses a tiny sensor inserted in the subcutaneous space to provide a simple and painless method of obtaining 288 glucose readings a day and needs only 2 fingersticks a day for calibration. There are two forms of CGM – blinded and real-time (RT). The former collects the blood glucose information but does not permit the person wearing the device to see a graphic display of their data. In contrast, RT-CGM provides the data on a smart phone for patients to view in real time and is thought to promote behavior change because the user gets real-time feedback about the effect of their food choices and exercise on glucose levels.

There are a multitude of reasons for the significance and innovation of this protocol. Without weight loss, 15-30% of people with prediabetes may develop Type 2 diabetes within five years(1). In patients with diabetes, as little as 5% weight loss may significantly improve glycemic control (30). It has been hypothesized in previous studies that RT-CGM causes behavior modification in both Type 1 and 2 diabetes but few if any studies have objectively demonstrated how RT-CGM causes behavior modification or its use as a weight loss tool. Because of its simplicity, RT-CGM could be used in community/primary care clinics where other more intensive and complex interventions for weight loss may not be available. It could also be used in the adolescent population with new onset Type 2 diabetes as a teaching tool for both the adolescent and family unit. This would be the first study that would evaluate RT-CGM as a behavior modification and weight loss tool in patients with either prediabetes or diabetes. The DPP educational materials have not been evaluated outside of the core 12 weekly in-person intervention sessions which are time-consuming and costly. This study would provide evidence that a modified DPP approach was effective when combined with RT-CGM. Previous RT-CGM studies in Type 1 and Type 2 diabetes have not used standardized educational lifestyle materials with CGM teaching, which could help create a practice model to use in primary care/community clinics.

### C. Preliminary Studies

Many studies have demonstrated that RT-CGM can be used in adults and children with both Type 1 and Type 2 diabetes resulting in improvement in HbA1c and/or a reduced frequency of hypoglycemia (17-19). Table 2 shows the average blood sugars of normal, prediabetic, and diabetic patients (24). Our initial research showed that the use of RT-CGM serially over 3 months improved HbA1c by an average of 1.0% in subjects with Type 2 diabetes on no prandial insulin (20). Nutrition and activity changes were not measured but the 3-month HbA1c improvement was sustained for another 9 months without further RT-CGM intervention (21). We hypothesized that the RT-CGM data motivated the subjects to make salutary changes in their diet and exercise habits leading to this long-term improvement in HgA1c (20, 21). However, there has been little direct examination of RT-CGM as a behavior modification/weight loss tool, as most studies have focused on HbA1c changes. Yoo et al. did show that intermittent use (3 days of RT- CGM every month for 12 weeks) produced a significant decrease in calorie

Page 2 of 14

consumption, increase in physical activity, improvement of weight, and a 1% decrease in HbA1c in poorly controlled patients with Type 2 diabetes (22). Allen et al. found that the data from a single three-day session of blinded CGM when combined with subsequent counseling and review of the CGM glucose data with the patient resulted in an increase in physical activity and a decrease in HbA1c by 1.2% and BMI by 0.5 kg/m^2 (23). The only study using RT-CGM in patients with prediabetes showed significant glycemic variability at baseline but did not show decreased glycemic variability or improvement in weight after 6 months, and diet and activity levels were not measured (24, 25). The reasons for the failure to achieve weight reduction in that study may have been due to the lack of specific lifestyle counseling and/or instructions on use/interpretation of RT-CGM to the subjects. In addition, the rigorous RT-CGM schedule in the protocol (6 days of RT-CGM wear on 4 occasions over 3 months) may have been too intense for patients with prediabetes who are generally not even required to perform fingerstick blood glucose measurements.

In our original study on patients with Type 2 diabetes using RT-CGM, the mean, unadjusted HbA1c decreased by 1.0, 1.2, 0.8, and 0.8% in the RT-CGM group vs. 0.5, 0.5, 0.5, and 0.2% in the SMBG group at 12, 24, 38, and 52 weeks, respectively (P = 0.04). There was a significantly greater decline in HbA1c over the course of the study for the RT-CGM group than for the SMBG group, after adjusting for covariates (P < 0.0001, figure 1). Also, more people in the RT-CGM group experienced weight loss of >3 pounds in the 0- to 12-week time period compared with the SMBG group (P = 0.03, Table 1) (21). In the prediabetes study with RT-CGM significant glycemic variability (GV) was seen in prediabetes participants with Mean Amplitude of Glycemic Excursion: 50 +/- 18 mg/dL (24) as compared to other studies which showed excursions of 26-28 mg/dL in normal subjects and 75 +/- 28 mg/dL in patients with diabetes (31). However, the change in GV or weight loss was not significantly improved which was surprising as focus groups conducted after intervention were positive about the RT-CGM experience (25). Figure 2 is an example of a representative CGM tracing of a "normal" patient, a patient with prediabetes and one with diabetes. Behavior modifications were not evaluated in either the prediabetes or Type 2 diabetes RT-CGM study. The studies also did not assess whether blood sugars are affected by significant education about diet and exercise. We propose that further education on how to use RT-CGM will help facilitate weight loss and behavior modification. There are only two studies that have evaluated behavior modification changes in patients with Type 2 diabetes and none in the pre-diabetic population (see background above).

#### Figure 1: Mean HbA1c change from Baseline

Change equals later HbA1c minus baseline HgA1c. This figure shows the raw mean changes and SEMs A separate multilevel model of the actual HbA1c values, with a transformation of the time variable to reflect the deceleration of change over time (1/time, with time defined as 1–5), showed that the decline in A1c over the course of the study differed between the groups net of other factors known to cause A1c change: age, sex, diabetes therapy, and initiation of insulin(21).

	0–12 weeks			0-52 weeks		
	RT-CGM	SMBG	Р	RT-CGM	SMBG	Р
Weight loss (> $-3$ pounds)	20 (40)	9 (18)	0.03	23 (46)	17 (34)	0.37
No weight change	24 (48)	29 (58)		16 (32)	15 (30)	
Weight gain $(> +3 \text{ pounds})$	6 (12)	12 (24)		11 (22)	18 (36)	

### Table 1: Mean weight change by group CGM vs. SMBG (21)

Page 4 of 14

Figure 2: Representative Tracings of Patients with Prediabetes, Diabetes and Normal(24)

Normal mg/dl	PreDM mg/dl	T2DM mg/dl
+/- SD	+/- SD	+/- SD
100.0 +/- 16.4	119.9 +/- 25.5	141 +/- 41.8

Table 2: Average blood sugars of Patientswith Normal, Prediabetes, Diabetes (24)

### **D.** Research Design and Methods

The central premise of this intervention is that for RT-CGM to be effective as a behavior modification tool for weight loss in patients with prediabetes and diabetes it must include education on interpreting RT-CGM data in the context of appropriate initial lifestyle and weight reduction counseling. We are guided by Social Cognitive Theory, which specifies goal setting as an important strategy (26, 27). This approach has been widely used for understanding and researching behavior change. When specifically applied to nutrition education interventions it has been shown to be successful when the interventions are behaviorally focused and theory driven. Cullen et al. developed a goal-setting process, based on previous work to help dietitians use goal-setting strategies in nutrition counseling by: (1) recognizing a need for change; (2) establishing a goal; (3) adopting a goal-directed activity and self-monitoring; and 4) selfrewarding goal attainment (28, 29). We will follow a counseling protocol that was designed to change efficacy beliefs about diet and activity and follow this basic strategy. In the first session we will: (1) outline benefits of nutrition and activity as based on the DPP and discussed CGM patterns with each participant, i.e. the effect of food and activity on blood sugars; (2) set specific activity and calorie goals, and; (3) monitor with CGM. In the second session, we review and evaluate the CGM patterns and challenge the participants to improve their dysglycemic pattern (goal attainment). We have selected ten days' duration of RT-CGM over two sessions based on the limited previous studies and we anticipate this study will provide important insights on whether or not RT-CGM is effective as a behavior modification tool for weight loss in patients with prediabetes and diabetes.

A maximum number of 45 participants will be recruited that meet inclusion/exclusion criteria for the study. Recruitment information about the study will be made available to all medical personnel including medical assistants, nursing staff, and primary care providers at the

GW Medical Faculty Associates Internal Medicine clinic, Gynecology clinic, and Endocrine clinic by medical staff and provider flier (Appendix F). Information about the study will be made available to those patients by a Study Flier (Appendix H) which will provide them with contact information for the study coordinator. As well, if potential participants express interest in the study to medical staff at GW, permission for the study coordinator to contact them via telephone or email will be requested and potential participants will be contacted for further screening and potential enrollment. The Study Screening and research procedures will take place at the GW endocrine clinic. Subjects may also be identified through posters and flyers placed in the GW community. Potential subjects who satisfy the study criteria and express interest in the study will be given information about participation either by mail, email or a phone call, depending on their preference. Pre-screening questions will be asked but no study related procedure or screening questions will be performed until informed consent/authorization have been obtained (see Appendices D and L).

We propose to perform a prospective study of 45 participants that will involve 15 subjects (ages 18-55) who are obese (BMI>30) and have prediabetes with HbA1c 6.0-6.4%, and 15 obese (BMI>30) subjects with Type 2 diabetes (ages 18-55) and with HbA1c 7.0-10.0%. 15 subjects will be in the control group with either prediabetes (n=7) or diabetes (n=8). Subjects will be randomized to intervention or control through a computer-generated system. All eligible participants will be able to walk 2 city blocks at baseline. Patients with prediabetes will be on no medications for diabetes and patients with Type 2 diabetes will have to be on the same diabetes medication(s) for 3 months prior to enrollment. The medication regimen may include basal insulin but not premeal insulin. Uncontrolled diabetes A1c>10.1% will be excluded, as well as participants who are pregnant, lactating, enrolled in another weight loss program, or using a weight loss medication (see inclusion /exclusion criteria below). The study will be advertised by flyers in the GW Endocrine Clinic, Internal Medicine Clinic, and also advertisements in the local newspaper.

### Inclusion criteria:

- 1. Age 18-55
- 2. Prediabetes (A1c 6.0-6.4) or Diabetes (A1c 7.0-10)
- 3. BMI ≥ 30 kg/m2
- 4. Willing to wear pedometer during study period
- 5. Able to walk 2 city blocks at baseline without assistance (self-reported)
- 6. Reading level at least 6th grade in English
- 7. Expected to remain in local community for at least 4 months

Page 6 of 14

- 8. Either is not treated with or has been on a stable treatment regimen of any of the following medications for a minimum of 3 months prior to Visit 1 (Screening/Enrollment):
  - a. Sulfonylureas
  - b. Biguanidine
  - c. Thyroid replacement therapy
  - d. Glp-1 agonists
  - e. Sodium-glucose co-transporters
  - f. Basal insulin
  - g. Thiazolidinediones
  - h. Hormone replacement therapy (female subjects) estrogen/progesterone products
  - i. Oral contraceptives/birth control (female subjects)
  - j. Antidepressant agents (SSRIs, Paxil, Prozac, Celexa, Zoloft, etc.)
- 9. Is able to read, understand, and sign the Informed Consent Form (ICF) and if applicable, an Authorization to Use and Disclose Protected Health Information form (consistent with Health Insurance Portability and Accountability Act of 1996 [HIPAA] legislation), communicate with the investigator, and understand and comply with protocol requirements

### Exclusion criteria:

- 1. Women who are pregnant, lactating, planning to become pregnant
- 2. Subjects who are taking amphetamines, anabolic, or weight-reducing agents
- 3. Contraindications to moderate exercise
- 4. Pre-prandial insulin
- 5. On any antipsychotic medication or history of schizophrenia or bipolar disorder
- 6. Daily use of any form of steroid medication (oral, inhaled, injected) within the last 3 months
- 7. Active wounds or recent surgery within 3 months
- 8. Inflammatory disease, or chronic and current use of anti-inflammatory drugs or narcotics
- 9. Active cardiovascular diseases within 12 months of Visit 1, such as myocardial infarction, clinically significant arrhythmia, unstable angina, coronary artery bypass surgery, or angioplasty; or are expected to require coronary artery bypass surgery or angioplasty during the course of the study
- 10. Presence or history of severe congestive heart failure (New York Heart Association Class IV [CCNYHA 1994])
- 11. Has evidence of current abuse of drugs or alcohol or a history of abuse that, in the investigator's opinion, would cause the individual to be noncompliant
- 12. Enrolled in another weight loss program
- 13. Already receiving continuous glucose monitoring (CGM)

Interested volunteers will be screened by telephone or in person in respective clinics and then scheduled for a screening visit week 0). If potential participants express interest, they will be provided an email address or phone number to call for more information. Alternatively, participants will be asked if they would like to be called to receive more information and are willing to provide their contact information to study staff. If after receiving more information, the potential participant is interested, then pre-screening questions (appendix D) will be asked. If still eligible, then a screening appointment will be arranged by study staff. If the participant is not interested in participating, a handout will be given for other sources for weight loss.

### Study Design (see Appendix C):

#### Screening/Pre-Intervention Visit:

Consent will be obtained prior to any screening procedures being completed, and conducted in a quiet room. Participant will be given ample time to ask questions, and a copy of the signed consent form will be given prior to start of screening visit.. Participants will fill out a contact form, including emergency contact. Study staff will review medical history and medications (through appendix E), as well as all inclusion/exclusion criteria. Vital signs will be collected, including height, weight, blood pressure, waist circumference, and resting heart rate. Body composition will also be assessed by bioelectrical impedance using a Tanita scale. A urine pregnancy test (if applicable), lipid panel, and HbA1c, both point of care (fingerprick) and serum, confirmed via LabCorp, will be obtained to determine prediabetes or diabetes. Approximately 1 teaspoon of blood will be drawn. (Note: 10 hour fasting labs will be required for Weeks 0 and 14. If the patient is not fasting, they can return the next day for fasting labs.) If a patient has an HbA1c documented in the medical record within 2 weeks of the pre-intervention session, then the point of care HbA1c will not be done. The available A1c will be used. If they meet all inclusion and exclusion criteria (as outlined above), they will be randomized into either the CGM intervention or control arm at the screening visit.

At the pre-intervention session (week 0) the control and CGM intervention groups (composed of both diabetics and prediabetics) will be asked to wear the CGM blinded for 10 days. They will be asked to continue their usual diet and activity and observe and record their physical activity and food intake on appropriate logs. They will be given a pedometer to track physical activity data, and be given other self-report questionnaires on their perception of CGM, physical activity, and nutrition. The 3-minute stair step test will be conducted. Week 0 consenting and baseline data/measurements will take between 1 hour 30 minutes to 2 hours.

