#### Weeks 2, 6

RT-CGM education and use will be coupled to one initial nutrition and exercise counseling session at Week 2 by the diabetes educator. Individually administered nutrition and exercise counseling will be based on a condensed version of the standard 12-session Diabetes Prevention Program Group Lifestyle Balance (DPP GLB, Appendix B) material and received by all participants. All those enrolled in the CGM intervention (N=30) will participate in 2 cycles of RT-CGM with direct feedback on CGM patterns at the second session, Week 2.

Both groups will then follow up and be given diet and exercise education handouts and instruction based on the DPP GLB core nutrtion and physical activity materials (Appendix B) at Week 2. The diabetes and prediabetes CGM intervention groups will also receive additional education on how food and exercise affects bloods sugar, and how to evaluate and respond to their blood sugar changes with RT-CGM (Appendix A). The CGM intervention participants will then wear the RT-CGM device for 10 days at week 2 and at 6 weeks. At week 2, CGM patterns will be reviewed with diet and food logs, and CGM intervention patients will be challenged "to beat their averages. The control group will review their diet and exercise log with the instructor and attempt to continue to make small changes in diet and exercise. Vital signs will be taken at each visit, including waist circumference. Pedometer data will be collected at weeks 6 and 14. Week 2 education on nutrition and RT-CGM will take 1 hour 30 minutes to 2 hours. Week 6 CGM review and measurements will take 1 hour. They will mail their sensors back from the continuous glucose monitoring device after 10 days, along with physical activity and food logs. They continue wearing their pedometers during this time.

Page 8 of 14

#### Week 14

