#### **Physical Activity Measurements:**

**Resting heart rate:** Participants will remain in a seated position for a miminium of 15 minutes prior to resting heart rate being taking with a Omron Professional Digital blood pressure and heart rate monitor.

**Three minute stair step**: Queens College Step Test: The Queens College Step test is one of many variations of step test procedures, used to determine aerobic fitness. Compared to the Harvard Step Test, this version has a lower step height, slower cadence, shorter test and more simple analysis (33).

**Pedometer data**: We will compare average steps per week at 14 weeks relative to baseline steps assessed in the first 2 weeks. After 14 weeks, we will assess the percentage of participants that attain a weekly goal of 10,000 steps daily for greater than 3 out of 7 days of the week. While we know of no validated reference for this, this goal was discussed with [name], FAHA, FACSM who is Director, Human Performance Research & Lifestyle Interventions for Veterans (LIVe) Veterans Affairs Medical Center, DC.

**Nutrition/Activity Questionnaires (Appendix I)**: Starting The Conversation (STC) is an eightitem simplified food frequency instrument designed and validated for use in primary care and

Page 10 of 14

health-promotion settings (34).

**Physical activity (Appendix J)**: The International Physical Activity Questionnaire (short) is a validated questionnaire that reviews the last 7 days of activity for middle aged adults (age 15-69 years) (35).

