### Collection of Human Biological Specimens:

**Fingerstick and serum HbA1c**: The HbA1c test is a blood test that provides information about a person's average levels of blood glucose over the last 3 months. The DCA Vantage Analyzer HbA1c assay tests for a quantitative determination of HbA1c in human whole blood, and provides immediate test results from a finger prick of blood. Serum HbA1c is sent via LabCorp. Urine HCG: HCG by urine dipstick will be collected prior to enrollment in study, if applicable. **Serum fasting lipids** will be collected at baseline and 14 weeks. This data will be provided to the participant to discuss further with their physician at the completion of the study when both pre and post labs are available.

**Perception of CGM (Appendices Q and R):** The Harvard Joslin Diabetes Center has developed a series of questionnaires on CGM experiences, opinions and expectations that will be given at the end of the intervention and has been adapted for the prediabetes population as well.

**CGM Data /Evaluation Measures:** Compliance/duration of participants with wearing CGM will also be recorded. Glucose dynamics, e.g., standard deviation, mean amplitude of glucose excursion (MAGE), and other statistical measures of glucose variability in those with prediabetes/diabetes/obesity with be reviewed from the CGM device data at baseline 2, 6 and 14 weeks

**Self perception/psychosocial questionnaires (Appendix K):** The Weight Efficacy Life-Style Questionnaire (WEL), Eating Habits and Exercise Confidence questionnaires will be given to patients at the beginning and end of the study to help evaluate any changes in self-perception after intervention (36-38).

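### Randomisation at week 0 comes before the baseline CGM and step windows, and nothing in the documents withholds the arm until the arms first differ at week 2

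*Protocol*

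**What the plan says.** The protocol's Screening/Pre-Intervention Visit section states that people who meet the criteria "they will be randomized into either the CGM intervention or control arm at the screening visit". The paragraph after the exclusion criteria dates that visit: volunteers are "then scheduled for a screening visit week 0".

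The next paragraph of the visit section already speaks of the two arms by name. Both "will be asked to wear the CGM blinded for 10 days", and the text continues: "They will be asked to continue their usual diet and activity and observe and record their physical activity and food intake on appropriate logs". A pedometer is handed out at the same visit. Physical Activity Measurements compares week-14 steps "relative to baseline steps assessed in the first 2 weeks". The CGM evaluation paragraph says that variability measures are "reviewed from the CGM device data at baseline 2, 6 and 14 weeks".

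The arms first diverge under Weeks 2, 6. There only the intervention arm gets the added glucose education, and "The CGM intervention participants will then wear the RT-CGM device for 10 days at week 2 and at 6 weeks".

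On concealment, section D says only that randomisation is computer-generated. The word blinded is used for the CGM display: section B explains that this mode "does not permit the person wearing the device to see a graphic display of their data". It says nothing about hiding the arm. The SAP takes the time main effect as the effect of interest, with N=30.

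**The concern.** A baseline should be fixed before the participant can react to the allocation. Here two baselines are behavioural, or driven by behaviour, and both are gathered in the fortnight after allocation. A participant who knows that RT-CGM is coming may start early or may put off effort until the device arrives. One who knows that it is not coming may lose interest or compensate. Staff who know the arm may coach differently.

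Either way the reference point moves. If the RT-CGM arm improves early, its later change is understated. If it postpones change, its later change is overstated. Because the shift would arise after allocation, randomisation does not balance it. What is at stake is the change in glycaemic variability (Aim 3) and the change in steps.

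**Working it through.** **1. Order of events**

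| Time | Event | Protocol section |
|---|---|---|
| Day 0 | Weight, waist, blood pressure, resting heart rate, body composition, HbA1c and lipids listed, then randomisation | Screening/Pre-Intervention Visit |
| About days 0–10 | Baseline blinded CGM, food and activity logs | Screening/Pre-Intervention Visit |
| About days 0–14 | Baseline steps | Physical Activity Measurements |
| Week 2 | First difference between arms | Weeks 2, 6 |

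The whole CGM baseline and essentially the whole step baseline follow allocation. The questionnaires and step test are mentioned after the randomisation sentence, but their order within the visit is not fixed, so no claim is made about them. The logs fall in the window, but the protocol describes them as returned for review and derives no outcome from them.

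**2. How large a shift would matter (illustration only)**

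The documents give no estimate of the shift, *b*. What can be worked out is the *b* that equals one standard error of the time effect for MAGE.

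Inputs:
- Section C gives MAGE of 50 ± 18 mg/dL in prediabetes and 75 ± 28 in diabetes. I read ± as an SD (assumption).
- Section D gives 15 intervention participants per diagnosis. The SAP's N=30 has the same 15 and 15 split, and I take it to be these people (assumption).
- The within-person correlation *r* is 0.5, range 0.3 to 0.7 (assumption).
- Data are complete, with a random-intercept model.

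*Baseline-to-week-14 contrast.* A shift *b* at baseline moves the change by *b*. SE = SD × √(2(1 − r)) / √n.
- Prediabetes: 18 × √1 / √15 = 4.65 mg/dL, and 4.65/50 = 9%.
- Diabetes: 28 × √1 / √15 = 7.23 mg/dL, and 7.23/75 = 10%.

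*Linear time over weeks 0, 2, 6 and 14.* The mean time is 22/4 = 5.5 and the deviations are −5.5, −3.5, 0.5 and 8.5. The sum of squares is 30.25 + 12.25 + 0.25 + 72.25 = 115.
- Carry-through to the fitted 14-week change: 14 × 5.5/115 = 0.67*b*.
- SE of the fitted 14-week change: 14 × √(SD² × (1 − r) / (n × 115)).
- Prediabetes: 14 × √(162/1725) = 4.29, so *b* = 4.29/0.67 = 6.4 mg/dL, or 13% of 50.
- Diabetes: 14 × √(392/1725) = 6.67, so *b* = 6.67/0.67 = 10.0 mg/dL, or 13% of 75.

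*Range.* Setting r at 0.7 or 0.3 multiplies every figure by 0.775 or 1.183.

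| One-SE shift, mg/dL | Prediabetes | Diabetes |
|---|---|---|
| Baseline to week 14 | 4.6 (3.6–5.5) | 7.2 (5.6–8.6) |
| Linear over four waves | 6.4 (5.0–7.6) | 10.0 (7.7–11.8) |

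The SAP does not say how time is coded, so both rows are possible. No SD is given for steps, so no figure is offered for them.

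**The case against.** The strongest reply is that this argues from silence. No passage says that anyone learns the arm at week 0, and the appendices and consent form are not in the material reviewed. That stands: a reader might infer that participants know their arm during the baseline window, and the documents do not support it. They support only that nothing withholds it.

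Second, the reach is narrow. A reader might extend the point to weight, or to the nutrition and activity outcomes of Aim 1. Weight and body composition are listed before randomisation. The named nutrition and activity instruments are questionnaires whose order relative to randomisation is not fixed, and no outcome is derived from the logs. This objection stands in full and limits the point to CGM variability and steps.

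Third, a shift of a tenth in MAGE from knowing the arm alone, with the display hidden and usual habits requested, is doubtful. Section C reports that the one prediabetes RT-CGM study did not reduce variability even with real-time display. This is fair but indirect. It concerns prediabetes only, section C itself suggests that missing lifestyle counselling may explain that study's failure to reduce weight, and it says nothing about steps.

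Fourth, the benefit is partial. Reactivity to the sensor, pedometer and logs occurs in both arms regardless, and participants know their arm from week 2 onward. This is also true. Late disclosure protects only the starting point.

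**Conclusion.** The point holds as a modest, avoidable risk: the stated sequence puts the CGM and step baselines after allocation, in an openly delivered behavioural trial, with no provision to withhold the arm. Size and direction are unknown, and no bias has been shown.

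The one-standard-error figures, roughly 9–10% of mean MAGE for a two-point contrast and 13% under linear time, rest on the assumptions listed. They show what would matter, not what is likely. A reader might take them as an expected distortion, or apply them to a comparison between arms. Neither is supported: the documents give no value for *b*, and the SAP plans no between-arm comparison. This is a cheap improvement, not a flaw that undermines the trial.

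**What to change.** Add after the randomisation sentence in the Screening/Pre-Intervention Visit section:

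*The allocation is held in the computer-generated randomisation system and is not disclosed to participants or study staff until the start of the week-2 visit, after the baseline CGM and step windows have ended and before any RT-CGM education.*

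Disclosure should depend on the windows having ended, not on mailed sensors or logs having arrived.

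An acceptable alternative is to generate the allocation at week 2. Section D and the Confidentiality section would then need to state whether the 45 (22 prediabetes, 23 diabetes) counts people enrolled or people randomised.

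The cost of the main option is one sentence. Both arms already follow the same steps to week 2, so no participants, visits or procedures are added. The downside is practical: staff must be ready to deliver either week-2 session without knowing the arm in advance. If the arm is already withheld in practice, the sentence simply records it.
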